### 4.3. Risk-Benefit Assessment

In an adequate and well-controlled 4-week Phase 2 study in adults with schizophrenia (Study SEP361-201), SEP-363856 demonstrated a statistically significant improvement in Positive and Negative Syndrome Scale (PANSS) total score compared to placebo with an effect size of 0.45, supporting antipsychotic efficacy. In an adequate and well controlled long-term, open-label extension study to Study SEP361-201, flexible treatment with SEP-363856 (25, 50, or

75 mg/day) resulted in continued improvements for up to 26 weeks in a broad array of symptoms of schizophrenia as measured by multiple effectiveness assessments.

Hypotension / orthostatic hypotension and syncope are potential risks associated with administration of SEP-363856 to subjects with schizophrenia. In general, events of hypotension / orthostatic hypotension experienced by the schizophrenia population have been transient, mild, or moderate in severity, non-serious, infrequently led to discontinuation of study drug, and did not require concomitant treatment or intervention. In general, events of syncope experienced by subjects with schizophrenia have been self-limiting, non-serious, transient (duration of the associated loss of consciousness [when reported] ranged between 10-20 seconds), moderate in intensity, did not lead to discontinuation of study drug, and did not require concomitant treatment or intervention.

### 5. STUDY OBJECTIVES

## 5.1. Primary Objective

• To evaluate the long-term safety and tolerability of flexibly dosed SEP-363856 (50, 75, 100 mg/day) in adult subjects with schizophrenia who have completed Study SEP361-308 by the incidence of overall adverse events (AEs), serious AEs (SAEs), and AEs leading to discontinuation.

## 5.2. Other Objectives

- To evaluate the long-term safety and tolerability of SEP-363856 by assessing:
  - o 12-lead electrocardiograms (ECG)
  - Vital sign measurements
  - Clinical laboratory tests
  - o Columbia Suicide Severity Rating Scale (C-SSRS)
  - o Simpson-Angus Scale (SAS)
  - o Barnes Akathisia Rating Scale (BARS)
  - Abnormal Involuntary Movement Scale (AIMS)
- To evaluate the long-term effectiveness of SEP-363856 using:
  - o Positive and Negative Syndrome Scale (PANSS)
  - o Clinical Global Impression-Severity (CGI-S) scale
  - o Clinical Global Impression-Improvement (CGI-I) scale
  - o Brief Negative Symptom Scale (BNSS)
- To evaluate the long-term effects of SEP-363856 on health-related quality of life as measured by the Short Form Health Survey (SF-12)
- To evaluate the long-term effects of SEP-363856 on functional capacity as measured by the Personal and Social Performance Scale (PSP)
- To evaluate long-term medication satisfaction as measured by the Medication Satisfaction Questionnaire (MSQ)
- To evaluate long-term sleep quality as measured by the Pittsburgh Sleep Quality Index (PSQI)
- To evaluate the long-term impact of SEP-363856 on healthcare resource utilization (HCRU)

### 6. STUDY ENDPOINTS

## **6.1.** Primary Endpoint

• The incidence of overall AEs, SAEs, and AEs leading to discontinuation

## **6.2.** Other Safety Endpoints

- Observed values and changes from Baseline of Study SEP361-308 (pre-switch baseline [PS Baseline]) and Baseline of Study SEP361-309 (open-label extension [OLE] Baseline) in clinical laboratory tests (including hematology, chemistry [including but not limited to lipid parameters and Hemoglobin A1c (HbA1c)], and urinalysis) (See Section 21)
- Observed values and changes from PS Baseline and OLE Baseline in vital signs (including temperature, body weight, body mass index [BMI], waist circumference, blood pressure [supine and standing], pulse rate [supine and standing] and respiratory rate) and 12-lead ECG parameters
- Frequency of subjects with suicidal ideation and suicidal behavior based on the C-SSRS
- Change from PS Baseline and OLE Baseline in SAS, BARS and AIMS scores
- Change from PS Baseline and OLE Baseline in PSQI scores

## 6.3. Other Endpoints

- Changes from PS Baseline and OLE Baseline in:
  - PANSS total score and subscale scores (positive, negative, and general psychopathology)
  - PANSS Marder Factor (five-factor) scores (positive, disorganized, negative, hostility, and depression/anxiety),
  - Uncorrelated PANSS (seven-factor) Score Matrix (UPSM) (positive, disorganized, negative apathy/avolition, negative deficit of expression, hostility, anxiety, and depression)
  - CGI-S score
  - o CGI-I score
  - o BNSS total score
  - o SF-12 score
  - o PSP score
  - MSQ score
- HCRU (including numbers of physician office visits, emergency room (ER) visits and hospitalizations, length of hospital stays, employment status and average number of hours caregiver spend helping subjects per week)
- Nicotine use

### 7. INVESTIGATIONAL PLAN

## 7.1. Overall Study Design

This is a 24-week, outpatient, multicenter, flexible-dose, open-label extension study designed to evaluate the long-term safety and tolerability of SEP-363856 (50 to 100 mg/day) for the treatment of subjects with schizophrenia who have completed Study SEP361-308 treatment period, during which they were switched from a previous antipsychotic treatment to SEP-363856.

The study will consist of two periods: An open-label extension (OLE) Treatment Period (up to 24 weeks), and a Follow-up Period visit at  $7 \pm 2$  days after last study drug dose for subjects who complete the Treatment Period and those who prematurely discontinue from the study (Figure 1).

Subjects who meet the entry criteria and choose to enter the extension study will transition immediately at the End of Treatment (EOT) visit from Study SEP361-308. Subjects who early terminate (ET) from the SEP361-308 study are not eligible to enroll in SEP361-309. The EOT visit from Study SEP361-308 will serve as the OLE Baseline visit for the present study. Informed consent will be obtained from all subjects before any study procedures are performed for the present study.

A study schematic is presented in Figure 1. Details of the study assessments and other procedures to be performed at each visit are presented in Table 2 Schedule of Assessments, and Section 11.6, Study Visits and Assessments. If necessary, subjects may return to the clinic at any time for an unscheduled visit at the discretion of the investigator.

Subjects will attend a Baseline visit on Day 1 (same day as the EOT visit of Study SEP361-308). Subjects will be seen at Baseline and then every 4 weeks thereafter up to Week 24. Telephone calls will be made by a qualified member of the clinical research staff to the subjects weekly between visits to administer the C-SSRS, collect AEs and concomitant medications, as well as to remind subjects about adherence to study drug administration and upcoming visits.

[figure not shown]

Figure 1: Study Schematic

Abbreviations: OLE = open-label extension.

All subjects will begin by receiving open-label SEP-363856 at the same dose they were taking upon completion of Study SEP361-308. Thereafter, the dose can be adjusted within the range of 50 to 100 mg/day, if deemed clinically necessary by the Investigator.

Dose adjustment criteria for SEP-363856 are described in Section 10.1.1.

For subjects who have received study drug and who prematurely discontinue from the study treatment, every effort should be made to complete procedures within 48 hours of the last study drug dose at the EOT/ET visit.

Safety and tolerability will be monitored throughout the study by collection of physical examination (PE) results, ECGs, vital signs, AEs, and clinical laboratory parameters. Sleep quality will be assessed using the PSQI, and suicidality will be assessed using the C-SSRS. Subjects who have any new significant findings or worsening of findings for suicidal ideation or behavior at any time during the study must be referred to the investigator for follow up evaluation.

Motor function will be assessed using the SAS, BARS and AIMS scales. HCRU will also be collected in this study.

Effectiveness will be evaluated using the PANSS total score and subscale scores, as well as CGI-S score and CGI-I score, BNSS score, and PSQI global scores. Function, quality of life, and treatment satisfaction will be assessed using the PSP, SF-12, and MSQ.

Population pharmacokinetic (POPPK) analysis will be performed using plasma SEP-363856 concentrations; the results of which will be reported separately.

## 7.2. Treatment Assignment and Blinding

### 7.2.1. Treatment Assignment

This is an open label, flexibly dosed SEP-363856 (50 to 100 mg/day) study.

#### 7.2.2. Blinding

This is an open label study.

### **7.2.3.** Emergency Unblinding Procedures

This is an open label study.

#### 7.3. Rationale

## 7.3.1. Rationale for the Study Design

This is an open-label extension study to further evaluate the long-term safety and tolerability of flexibly dosed SEP-363856 (50, 75 or 100 mg) over 24 weeks of treatment in subjects with schizophrenia who completed Study SEP361-308. Long-term effectiveness of SEP-363856 will also be evaluated.

### 7.3.2. Rationale for the Dosages

Selection of these doses was guided by the results from the development program to-date, including the maximum tolerated dose (MTD) determined for single doses of SEP-363856 administered to subjects with schizophrenia in Study SEP361-105 (100 mg); by the single doses administered to healthy adult subjects in Studies SEP361-103 and SEP361-104 (50 mg) which were found to have robust CNS activity and by Study SEP361-201, which demonstrated a statistically significant difference in change from Baseline to Week 4 in PANSS total score for SEP-363856 (50 to 75 mg/day flexible dose) versus placebo in adults with an acute exacerbation of schizophrenia and which showed that SEP-363856 at doses of 50 to 75 mg/day for up to 28 days was well-tolerated.

The MTD for multiple doses of SEP-363856 in adults with schizophrenia was previously determined to be 75 mg/day (Study SEP361-106). In Study SEP361-106, as more than 50% of SEP-363856 subjects in the 100 mg/day cohort (5 of 9 subjects) experienced multiple moderate AEs assessed as related to SEP-363856 the protocol defined MTD for multiple daily oral administration of SEP-363856 to adult subjects with schizophrenia was determined as 75 mg/day. The only moderate AEs assessed as related to SEP-363856 experienced by more than 1 subject in the 100 mg/day dose group were somnolence and dizziness, none of which resulted in treatment discontinuation.

However, in Study SEP361-201, where the majority of subjects received 75 mg/day for 4 weeks, the tolerability and safety profile was shown to be similar to that of placebo. This indicates that a dose higher than 75 mg/day may be tested to maximize efficacy, based on an acceptable expected benefit/risk ratio. In Study SEP361-201, subjects were required to receive 50 mg/day for at least 3 days before titrating up to 75 mg/day. The dose of 100 mg/day was chosen because it is the highest dose in the proposed therapeutic dose range being examined in the ongoing Phase 3 program (25 to 100 mg).

#### 7.3.3. Rationale for the Endpoints

The objective of this study is to demonstrate that clinically stable outpatients with schizophrenia who have completed a switch from their current antipsychotic treatment can be safely and effectively maintained on open-label treatment with SEP-363856 for a period of 24 weeks. The outcome measures include standard safety measures (eg, AE's, SAE's, measures of motor function, assessment of suicidality, laboratory assessments, and ECGs). Additional validated effectiveness assessments for schizophrenia (eg, PANSS, CGI-S) that were also employed in Phase 2 and Phase 3 studies of SEP-363856 are included for the purpose of providing longer-term effectiveness data. Additionally, measures assessing function, medication satisfaction, quality of life, sleep, and healthcare utilization are intended to provide information on real-world and overall health aspects associated with transitioning between treatments.

## 7.4. Prevention of Missing Data

In an effort to minimize the number of subjects who are terminated from the study prior to study completion, the following study design and conduct elements are implemented:

• Study is conducted as outpatient.

- Some concomitant psychotropic medications are allowed, as needed, during study participation.
- Dose reductions of SEP-363856 are allowed for drug tolerability purposes.
- Study centers are chosen based on a strong record of enrolling and retaining eligible subjects and producing quality data.
- Study centers are trained on the importance of continued follow-up and on the informed consent process, ensuring subjects understand the commitment they are making, including the intent to complete the trial.
- Telephone calls will be made by a qualified member of the clinical research staff to the subjects weekly between visits that are more than one week apart to administer the C-SSRS, collect AEs and concomitant medications, as well as to remind subject about adherence to study drug administration and upcoming visits (Section 11.6.8).
- Data collection is monitored at the site level for adherence during the study.

See Section 15.3.10 for statistical considerations related to missing data.

### 8. SELECTION OF SUBJECTS

## 8.1. Subject Inclusion Criteria

To qualify for participation, subjects must meet all of the following inclusion criteria:

- 1. Subject must give written informed consent and privacy authorization prior to participation in the study and be able to comply with the protocol, in the opinion of the investigator. Separate consent will be obtained from a caregiver or legal guardian if required by local law.
- 2. Subject has completed the Treatment Period of Study SEP361-308.
- 3. Subject has not taken any psychotropic medication other than the study drug, pre-switch antipsychotic and protocol-allowed medications described in Section 10.3.3 during Study SEP361-308.
- 4. Female subject must have a negative rapid urine pregnancy test at the End of Treatment (EOT) Visit of Study SEP361-308.
- 5. Female subjects of childbearing potential must agree to use acceptable effective and reliable contraception throughout the study and for at least 30 days after the last dose of study drug has been taken. In the Investigator's judgment, the subject will adhere to this requirement. Contraception requirements are detailed in Section 10.4.
- 6. Male subjects must agree to avoid fathering a child and use acceptable effective methods of birth control from screening in Study SEP361-308, until at least 30 days after the last study drug administration in the present study (SEP361-309). Contraception requirements are detailed in Section 10.4.

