Male subjects with a female partner(s) of childbearing potential must agree to avoid fathering a child and must be surgically sterile (with the appropriate post-vasectomy documentation of the absence of sperm in the ejaculate) or use acceptable effective methods of contraception from Screening in Study SEP361-308 until at least 30 days after the last dose of study drug. Male subjects must also refrain from donation of semen/sperm 30 days prior to administration of the first dose of study drug, during the Treatment Period and for 30 days after last dose of the study drug.

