# 12.4.2. Pregnancy

Pregnancies that occur from the time that informed consent is signed through 90 days following the last dose of the study medication will be collected and reported on the Pregnancy Event Form.

If a subject becomes pregnant during the course of the study, she will be instructed to stop taking the study medication. Further, the subject will be instructed to return to the study center within 48 hours of the first notification of pregnancy and undergo a serum pregnancy test, as confirmation of pregnancy. If positive, the female pregnant subject will no longer receive any additional study medication. All pregnancies, whether or not the subject received any additional study medication, will be followed until resolution (ie, termination [voluntary or spontaneous] or birth). Infants may be followed for up to one year following birth.

If a pregnancy is reported for a study subject's partner from time of subject's first dose to 30 days post last dose, the subject's partner may be asked to sign a consent form to allow the Sponsor to follow her pregnancy. The Sponsor's representative will provide instructions on how to collect pregnancy information in accordance with local requirements. Proper consent to collect the partner's information will be obtained before the collection of any information.

To report a pregnancy, the Pregnancy Event Form must be completed and sent via fax to PPD-PVG immediately but no more than 24 hours after the Investigator or study center staff becomes aware of the pregnancy. The Sponsor provides the Pregnancy Event Form.

Pregnancy itself is not regarded as an AE unless there is a suspicion that the study drug may have interfered with the effectiveness of a contraceptive medication or other AEs were detected.

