# 13.2. Clinical Assessments After Study Drug Discontinuation

Subjects who have not received any study drug will not be followed up on leaving the study.

For subjects who have received study drug and who prematurely discontinue from the study treatment (ie, do not complete through Week 24), every effort should be made to complete the final evaluation procedures, in accordance with the ET visit described in Section 11.6.7.

Subjects who complete the study and those subjects who discontinue the study early will complete a follow up visit 7 (±2) days after the last dose of study drug as described in Section 11.6.9.

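### Partner-pregnancy follow-up is tied to a report by 30 days after the last dose, the day the male contraception window ends; that leaves no time for recognition, and the 90-day sentence in Section 12.4.2 does not say whether it covers partners

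*Protocol*

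**What the plan says.** Three limits after the last dose bear on this point.

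- **Male contraception.** Section 8.1, criterion 6, applies "from screening in Study SEP361-308, until at least 30 days after the last study drug administration in the present study (SEP361-309". Section 10.4 agrees: men with a partner of childbearing potential must be surgically sterile or "use acceptable effective methods of contraception from Screening in Study SEP361-308 until at least 30 days after the last dose of study drug".
- **Partner pregnancies.** The provision in Section 12.4.2 that names partners begins "If a pregnancy is reported for a study subject's partner from time of subject's first dose to 30 days post last dose". In that case "the subject's partner may be asked to sign a consent form to allow the Sponsor to follow her pregnancy".
- **Pregnancies in general.** Section 12.4.2 opens with "Pregnancies that occur from the time that informed consent is signed through 90 days following the last dose of the study medication", which are to be collected on the Pregnancy Event Form. It does not say whether this includes partners. A later sentence says "All pregnancies, whether or not the subject received any additional study medication, will be followed until resolution", but it stands in the paragraph on female subjects who become pregnant.

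Under Section 13.2, subjects who complete and those who stop early "will complete a follow up visit 7 (±2) days after the last dose of study drug". That is the last scheduled contact.

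**The concern.** A pregnancy can be reported only after it has begun and been recognised. Sections 8.1 and 10.4 treat a conception up to 30 days after the last dose as one to be avoided. The partner rule then closes to reports on that same day. On the literal text, a partner who conceives late in the risk window will be recognised too late for the consent request that Section 12.4.2 describes.

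The 90-day sentence does not settle the matter. It uses another limit and another basis (occurrence instead of report), and it is silent on partners. A site that learns of a partner pregnancy on day 45 after the last dose could find support for collecting it in one sentence and no stated basis for asking the partner's consent in another. What is at stake is outcome information on pregnancies that the protocol itself regards as potentially exposed, for a drug still in development.

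**Working it through.** Days are counted from the last dose of study drug; negative days are on treatment. The protocol states no figure for this point, so there is none to reproduce.

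**Inputs**

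- End of male contraception window: C = 30 (Sections 8.1 and 10.4; both say at least 30 days).
- Last day for a partner report, read literally: R = 30 (Section 12.4.2).
- Last day for a pregnancy to occur under the general sentence: 90 (Section 12.4.2).
- Last scheduled contact: 7 ± 2, that is day 5 to day 9 (Section 13.2).
- Lag from conception to report: L. The protocol does not give it. Values from 14 to 56 days are assumed here for illustration.

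**Room for recognition and reporting**

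R - C = 30 - 30 = 0 days. Any L above zero therefore leaves a gap, whatever its value.

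**Latest conception that can be reported in time**

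Latest day = R - L.

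| Assumed L (days) | R - L | Conceptions in the risk window reported too late |
|---|---|---|
| 14 | 30 - 14 = 16 | after day 16: the last 14 of the 30 post-dose days |
| 28 | 30 - 28 = 2 | after day 2: the last 28 of the 30 post-dose days |
| 42 | 30 - 42 = -12 | all post-dose days and the last 12 days on drug |
| 56 | 30 - 56 = -26 | all post-dose days and the last 26 days on drug |

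Once L exceeds 30 days, the gap reaches back into treatment.

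**Effect of the visit schedule**

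No scheduled contact falls after day 9, so any report between day 10 and day 30 depends on the subject or partner coming forward. If reports came only at the last scheduled contact, R would be at most 9 and the gap would be wider.

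**Check of the proposed change**

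If the partner window is defined by conception through C = 30 and a later report still triggers the request, a conception on day 30 qualifies for every L in the table.

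**The case against.** The strongest reply is that the gap comes from one reading of one sentence. The 30-day phrase may have been meant to describe when the pregnancy occurs. The partner window would then end with the contraception window and the gap would close. That may be the intention, but the sentence attaches the period to the report. This objection supports clarifying the text; it does not show that the text is clear.

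A reader might go further and infer that later partner pregnancies are never followed and that their outcomes disappear from the safety record. The protocol does not support that. Section 12.4.2 does not forbid follow-up of a later report. Its 90-day sentence is not restricted to female subjects, and the 24-hour rule for submitting the form has no end date, so a later partner pregnancy might well be collected. There is also a partial route through Sections 12.1.2 and 12.4.1: congenital anomaly is a seriousness criterion, and a possibly related serious event learned of more than 30 days after the last dose is still reportable, although that text is not written for partners' infants. What remains open is the consent request, for which no basis after day 30 is stated.

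Two other tempting steps also fail. Subtracting 30 from 90 does not give female subjects 60 days for recognition, because the 90-day sentence counts occurrence and sets no report deadline. Nor can the gap be stated as a share of exposed pregnancies: the lag is assumed, and a share of calendar time is not a share of pregnancies.

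The practical gain is modest. Follow-up of a partner is optional even inside the window, and reports after day 9 are passive under any cut-off.

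**Conclusion.** The point holds as a limited defect of drafting in Section 12.4.2. Sections 8.1 and 10.4 agree with each other and need no correction; they supply the limit against which the partner rule falls short. On the literal text the room for recognition is 0 days. That result needs no outside figure, only the fact that a report follows conception. How far back the gap reaches does depend on the lag: under the assumed 14 to 56 days, it ranges from the last 14 post-dose days to the whole post-dose window plus the last 26 days on drug.

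Separately, the 30-day and 90-day limits within Section 12.4.2 either conflict for partners or leave their coverage unclear.

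The consequence is small. About 67 subjects are expected, the protocol does not give the share of men, and contraception is required. The primary endpoint, the safety population and the sample size are unaffected. This is a desirable correction, not an essential one.

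**What to change.** In Section 12.4.2:

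1. Define the partner window by when the pregnancy occurs (estimated conception), at least through the end of the male contraception window in Sections 8.1 and 10.4, instead of by the date of report.
2. State that a later report of such a pregnancy still triggers the request for the partner's consent.
3. State whether the opening 90-day sentence covers partners.
4. Align the consent wording with the result.

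This changes safety reporting only. The contraception requirement, the visit schedule and the study procedures stay as they are. The cost is a small edit to one section and its matching consent text, and an occasional extra Pregnancy Event Form for sites.
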